A syndrome of acute cholecystitis with right upper quadrant pain and nausea and vomiting in HIV-infected patients receiving rIL-2 was described by Powell and coworkers (47). By ultrasound, the gallbladder was noted to be thickened and no calculi were observed. Symptoms resolved with cessation of rIL-2 therapy, and surgery was not required.

Thyroid function abnormalities have been reported in participants receiving IL-2 treatment for malignancies (48-54) and for HIV (19, 33, 37, 42, 55). The reported frequency of thyroid abnormalities among persons receiving IL-2 has varied from 2.5 to 47%, but early reports included participants who received much larger doses than those planned in this study, administered intravenously, and often in combination with other immunomodulatory therapies such as lymphokine-activated killer (LAK) cells (48, 49) or interferon alfa. Among HIV-infected participants receiving subcutaneous rIL-2, the frequency of thyroid dysfunction in small studies has been reported to be between 2.5 and 11.7% (33, 37, 56). The two largest trials of rIL-2 among HIV-infected participants (42), however, did not specifically report the frequency of thyroid dysfunction, but senior investigators in those teams estimate the frequency to be between 10 and 15% ([name], [name], [name], [name], verbal communications).

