The purpose of this pilot study is to observe the effects of up to eight 8-weekly cycles of subcutaneous recombinant interleukin-2 (SC rIL-2) on levels of replication-competent HIV in blood CD4 T cells in 20 participants with chronically suppressed HIV infection (viral load <50 copies/mL) who are stable on the same ART regimen for at least one year and have a CD4 T cell count ≥ 350 cells/mm³. We hypothesize that IL-2 administration will result in a reduction of the replication-competent reservoir, as measured by the QVOA assay, compared to the baseline values in this population.

B.1. STUDY ENDPOINTS AND OUTCOME MEASURES

The primary endpoint of the study is the change in the level of replication-competent virus from baseline to the end of rIL-2 treatment, as measured by the Quantitative Viral Outgrowth Assay (QVOA).

B.2. PRIMARY OBJECTIVE

The primary objective will be to compare levels of replication competent HIV in circulating CD4 T cells before and after up to 8 cycles of rIL-2 administration. The frequency of CD4 T cells containing replication-competent virus in leukapheresis samples obtained at baseline and at the end of rIL-2 treatment will be enumerated using several state of the art methods. The primary readout for this objective will be measurement of replication-competent virus by Quantitative Viral Outgrowth Assay (QVOA) performed by [name]'s group at Accelevir.

B.3. SECONDARY OBJECTIVES

- 1) To examine the relationships between levels of replication competent HIV as identified by QVOA and other measures of HIV persistence:
 - a) the intact proviral DNA assay ([name]),
 - b) the Envelope Detection by Induced Transcription-based Sequencing (EDITS, [name]) performed on the same pre-trial and post-trial leukapheresis samples.
- 2) To explore the effects of rIL-2 administration on induction of HIV expression in vivo as measured by the EDITS assay and plasma HIV levels.
- 3) To examine the effects of rIL-2 administration on natural killer cell phenotype and function and on the ability of NK cells to limit HIV propagation in vitro.

C. METHODS

C.1. STUDY DESIGN

This is an open label pilot study of 20 participants with chronically suppressed HIV infection (viral load <50 copies/mL), stable on an ART regimen for at least one year, who have a CD4 T cell count ≥ 350 cells/mm³. All participants will receive rIL-2.

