All participants will receive rIL-2, 5 million units (MU) subcutaneously (SC) twice a day \times 4 consecutive days, every 8 weeks, for 8 cycles in addition to ART.

Ideally, rIL-2 doses should be 10 – 12 hours apart, but no closer than 6 hours, and no greater than 18 hours apart.

If at any point rIL-2 is discontinued, efforts will be made to maintain follow-up for all data collection as outlined in the schedule of events.

C.2. STATISTICAL CONSIDERATIONS

C.2.1. Analytic Plan

The primary analysis will test whether the change in the size of the replication-competent reservoir, as measured by the modified QVOA assay, from baseline to two weeks after the last rIL-2 infusion is significantly different than is expected by random variation. In this intent-to-treat analysis, all participants who received at least one dose of IL-2 will be included. Secondarily, we will perform an on-treatment analysis including only the subset of participants who received all eight planned IL-2 cycles. We will use mixed effects models to estimate the effect of IL-2 treatment on the replication-competent reservoir among all participants, controlling for possible confounding factors including at a minimum CD4 T cell count at baseline and at pre-ART nadir, duration of virologic suppression, type of antiretroviral regimen at study entry, historical peak plasma HIV RNA, and demographic factors.

We will then fit the relevant models to address the following secondary objectives:

- a. Replicate the analyses above in the on-treatment population, i.e., those who received all 8 planned IL-2 cycles.
- b. In the intent-to-treat population, add a term indicating the number of IL-2 cycles each participant received. This will account for variability of total dose, and the associated parameter and its interaction to time point will provide an estimation of the effect modification expected from repeated dosing. We will assess for non-linearity of any dose effect both graphically and formally, and fit higher-order terms as suggested by those analyses, to explore whether there is a threshold effect (i.e., whether the effect size changes drastically past a given number of doses), an analysis that was not reported in the original Chun paper.

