- Delivery of pre-filled cycle doses of rIL-2 and review of handling, storage, and administration procedures
- CBC and metabolic panel
- Thyroid function tests and anti-Tpo antibodies
- CD4+ and CD8+ T cell count (both absolute and as percent of lymphocytes)
- Plasma HIV RNA level by PCR (using the locally available assay)
- PBMC will be cryopreserved for assays of immune cell phenotype and NK cell phenotype
- Plasma will be cryopreserved for single copy HIV RNA assay
- The participant will be observed as he/she administers the dose of rIL-2 (approximately 5 million units) subcutaneously.

D.2.6. rIL-2 Treatment Cycles 4 and 8, Day 7

Participant returns to clinic for:

- Interval history and complete physical examination.
- Concomitant medication review
- Tolerance and compliance with injection schedule
- CBC and metabolic panel
- CD4+ and CD8+ T cell count (both absolute and as percent of lymphocytes)
- Plasma HIV RNA level by PCR (using locally available assay)
- PBMC will be cryopreserved for assays of immune cell phenotype and NK cell phenotype
- Plasma will be cryopreserved for single copy HIV RNA assay

D.2.7. rIL-2 Treatment Cycles 2 and 3, Day 0

NOTE: Each treatment cycle should begin 7-10 weeks after start of last treatment cycle. These visits will include:

- Interval history and targeted physical examination, including weight.
- Concomitant medication review.
- Delivery of pre-filled cycle doses of rIL-2 and review of handling, storage, and administration procedures

- CBC and metabolic panel
- Thyroid function tests and anti-Tpo antibodies
- CD4+ and CD8+ T cell count (both absolute and as percent of lymphocytes)
- Plasma HIV RNA level by PCR (using the locally available assay)
- IL-2 immunogenicity (cycle 2 only)

D.2.8. rIL-2 Treatment Cycles 5, 6, and 7, Day 0

NOTE: Each treatment cycle should begin 7-10 weeks after start of last treatment cycle. These visits will include:

- Interval history and targeted physical examination, including weight.
- Concomitant medication review.
- Delivery of pre-filled cycle doses of rIL-2 and review of handling, storage, and administration procedures
- CBC and metabolic panel
- Thyroid function tests and anti-Tpo antibodies
- CD4+ and CD8+ T cell count (both absolute and as percent of lymphocytes)
- Plasma HIV RNA level by PCR (using the locally available assay)

D.2.9. rIL-2 Treatment cycles 1-8, Days 2 and 4

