Staff will contact the participant by phone to assess tolerance and compliance with injection schedule

D.2.10. End of Study Visit (or Premature Discontinuation Visit)

NOTE: The end of study visit should take place 8 weeks (+/- 2 weeks) after Day 0 of the last (8th) treatment cycle. In the case of premature discontinuation, the end of study visit should take place at least 6 weeks after day 0 of the last treatment cycle and may take place up to 10 weeks after day 0 of the last treatment cycle.

These visits will include:

- Interval history and targeted physical examination.
- Immunogenicity testing
- CD4+ and CD8+ T cell count (both absolute and as percent of lymphocytes)
- Plasma HIV RNA level by PCR (using the locally available assay)
- IL-2 immunogenicity
- At this visit the participant will undergo a 4 Liter leukapheresis at the Seidman Ambulatory Stem Cell Transplant Unit at University Hospitals using AIDS protocol 328.
- Plasma will be cryopreserved for single copy HIV RNA assay
- Leukapheresis product PBMC will be cryopreserved for:
 - HIV reservoir assay by EDITS
 - HIV reservoir assay by QVOA
 - Total and intact proviral DNA assay (Accelavir)
 - Assays of immune cell phenotype and NK cell phenotype

If leukapheresis cannot be done after premature treatment discontinuation for any reason, a 120 cc. blood draw will be obtained for preparation of PBMC and plasma. Based upon cell yield these samples will be used for:

- Plasma will be cryopreserved for single copy HIV RNA assay
- HIV reservoir assay by EDITS
- HIV reservoir assay by QVOA
- Total and intact proviral DNA assay (Accelavir)
- Assays of immune cell phenotype and NK cell phenotype

D.2.11. Immunogenicity follow-up

Participants who have detectable neutralizing antibodies at the end of study visit will be followed approximately every 90 days for repeat testing until 12 months after the end of study or until a negative result is obtained. During these visits, an interval medical history and targeted physical exam will be conducted. If clinically significant events have occurred, the participant will be referred for appropriate medical care.

D.2.12. Management of off-window visits

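### Secondary analysis (b) cannot identify a dose-response or a threshold: everyone is assigned eight cycles, QVOA has one post-treatment sample, and cycle number is not assigned

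*Combined protocol and SAP*

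**What the plan says.** - **Assignment.** Section C.1 gives every participant the same course: "every 8 weeks, for 8 cycles in addition to ART". No variation in cycle number is planned or randomised.
- **Sampling.** Section B.2 measures the primary readout "in leukapheresis samples obtained at baseline and at the end of rIL-2 treatment". D.2.2 banks the pre-treatment QVOA sample and D.2.10 the post-treatment one. Between them, D.2.4 adds EDITS at cycle 1 day 7, and the cycle 4 and cycle 8 visits (D.2.5, D.2.6) store cells for phenotyping; neither provides QVOA.
- **Early stoppers.** D.2.10 says: "In the case of premature discontinuation, the end of study visit should take place at least 6 weeks after day 0 of the last treatment". The upper limit is 10 weeks. If leukapheresis cannot be done, a 120 cc draw replaces it. D.2.13 also lets single cycles be cancelled for clinical or logistical reasons.
- **Analysis.** C.2.1 item b enters the cycle count and states that "its interaction to time point will provide an estimation of the effect modification expected from repeated dosing". It will then "fit higher-order terms as suggested by those analyses, to explore whether there is a threshold effect", and presents this as something the source study did not report.
- **Covariates.** The minimum list in C.2.1 covers CD4 count (baseline and nadir), duration of suppression, regimen type, peak HIV RNA and demographics. Reason for stopping, time between samples and sample type are not named.

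**The concern.** The question asked is causal: does the effect on the reservoir change as more cycles are given, and is there a point beyond which it changes sharply? Answering it needs either people assigned to different numbers of cycles or repeated QVOA measurements in the same person as cycles accumulate. The design has neither. What the model tests is whether people who ended with fewer cycles had the same mean change as people who received all eight.

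People get fewer cycles for reasons: thyroid abnormality, serious infection, an antiretroviral interruption of more than four weeks (F.1), their own request, or a cancelled cycle. An antiretroviral interruption could itself bear on the reservoir. Fewer cycles also means an earlier second sample and possibly a smaller one. A non-zero coefficient could come from any of these, and a coefficient near zero would say little because it is poorly estimated. At stake is what the trial may conclude about repeated dosing.

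**Working it through.** **1. What the interaction estimates.** With two time points and a participant intercept, let C be cycles received and t be 0 before and 1 after treatment:

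Y = a(participant) + b·t + g·C + d·C·t, so change = b + d·C.

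The interaction d is the slope from regressing each person's change on cycles received. On one simulated data set both fits gave −0.078 (SE 0.058). No within-person dose information enters.

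**2. Time between samples.** The baseline leukapheresis is 4–8 weeks before cycle 1 (D.2.2). The final sample is 6–10 weeks after day 0 of the last cycle (D.2.10).

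- One cycle: 4 + 6 = 10 to 8 + 10 = 18 weeks.
- Eight cycles at 8-week spacing: add 7 × 8 = 56, giving 66 to 74 weeks.

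Among people who stop early, each further cycle adds about 8 weeks, so cycles and elapsed time rise together. Adding elapsed time as a covariate would leave little to separate them.

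**3. The plan's own power figure.** The documents state power only for the primary pre/post comparison: effect 0.64 IUPM, variance 0.41, 80% power, at 16 participants in the synopsis and 20 in C.2.2. Alpha is not stated; I take two-sided 5%. Power ≈ Φ(0.64·√N / SD of change − 1.96).

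- Variance of change 2 × 0.41 = 0.82 (no pre/post correlation), N = 16: 0.64 × 4 / 0.906 = 2.83, power 0.807. This recovers the stated 80%.
- Same variance, N = 20: 0.885.
- Variance of change 0.41, N = 20: about 0.99.

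So 0.82 is the value consistent with the stated 80% at 16 participants. I carry 0.82 and 0.41, and also 0.22 (twice the 0.11 quoted for the optimised assay).

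**4. Precision of item b.** No document gives the proportion receiving fewer than eight cycles. The nearest figure is thyroid dysfunction in A.5, where "senior investigators in those teams estimate the frequency to be between 10 and 15" percent. I assume 10–40%, with stoppers spread evenly over 1–7 cycles. At 15%, 20 × 0.15 = 3 people are expected below eight cycles. At 10%, 0.9^20 = 12% of trials have nobody below eight, so the term cannot be estimated.

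Power at N = 20, two-sided 5%, linear cycle term (simulation, 20,000 trials per cell; separate runs differ by about one point):

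| True effect | Variance of change | 10% | 15% | 25% | 40% |
|---|---|---|---|---|---|
| Linear, 0.08 per cycle (0.64 over eight) | 0.82 | 7% | 9% | 11% | 13% |
| | 0.41 | 10% | 13% | 18% | 23% |
| | 0.22 | 15% | 21% | 29% | 37% |
| Step of 0.64 after cycle 4 | 0.82 | 9% | 12% | 15% | 20% |
| | 0.41 | 15% | 19% | 26% | 34% |
| | 0.22 | 23% | 30% | 42% | 54% |

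Detectable slope with 80% power = (1.96 + 0.84)·√(variance of change / (20 × Var C)). At 10% stopping, Var C = 0.9·64 + 0.1·20 − 7.6² = 1.84; at 40%, 0.6·64 + 0.4·20 − 6.4² = 5.44. At variance 0.82 the detectable effect over eight cycles is 3.35 and 1.95 IUPM respectively; at 0.41 it is 2.37 and 1.38. All exceed twice 0.64.

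**5. Rejection when dose has no effect.** Everyone is given the same 0.64 fall whatever the cycle count.

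- Cycle number unrelated to response: about 5%.
- Latent correlation 0.3 between stopping and change: about 9–14%.
- Latent correlation 0.5: about 18–31%.
- If the timing of the stop follows the same latent variable, these become 10–18% and 21–47%.

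The correlations are assumed.

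**6. Data-driven shape.** As a stand-in for the unspecified threshold step, a search for the best cut-point, at variance 0.82 with cycle number unrelated to response, rejects in 4% of trials at 10% stopping and 14% at 40%.

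**The case against.** **Item b is secondary, in a pilot, and its threshold step is worded as exploration.** This stands in part. Low power for an exploratory term with 20 people is unremarkable, the plan claims no power for item b, and low power alone would not justify a change. But the statement that the interaction will estimate how the effect is modified by repeated dosing is not hedged, and no caution about unassigned cycle number accompanies it.

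**Cycle number does not vary only by early stopping.** Correct. Cancelled cycles, including logistical ones, also contribute. The comparison is still unassigned and between people.

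**The covariate list is only a minimum.** True, so reason for stopping and sample type could be added. With about three people below eight cycles at 15%, adjustment would be nominal, and elapsed time largely moves with cycle count.

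Three stronger readings are tempting, and the documents do not support them:

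- *Item b will produce false positives.* The excess for the linear term appears only if cycle number is related to QVOA change, and no figure in the documents supports a correlation of 0.3 or 0.5. Two titles in the reference list touch on whether thyroid toxicity goes with response to IL-2, but they concern cancer treatment and say nothing about the HIV reservoir.
- *Cells stored at cycles 4 and 8 could answer the dose question.* D.2.5 assigns them to another purpose ("PBMC will be cryopreserved for assays of immune cell phenotype and NK cell phenotype"), yields are not given, a different assay would replace QVOA, and within a single arm cycle number is again tied to elapsed time.
- *The primary comparison is undermined.* It does not use the cycle term.

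**Conclusion.** The point holds as a limit on what item b may conclude. Identification fails by design: uniform assignment and one post-treatment QVOA sample make the cycle term a non-randomised contrast between people, mixed with reason for fewer cycles, elapsed time and possibly sample type. This rests on the protocol's text and needs no numerical assumption.

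Imprecision is a second, supporting reason. Its figures depend on the assumed 10–40% below eight cycles, the even spread of stopping over cycles 1–7, and the variance of change; at the lowest variance and highest stopping rate considered, power for a linear effect is still only 37%. Type I error above 5% for the linear term is conditional on an assumed link between cycle number and response and should be reported only as such.

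**What to change.** In C.2.1 item b, replace the claim about effect modification and threshold with wording such as:

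> A hypothesis-generating description of change in QVOA by number of cycles received, using one pre-specified linear term with its confidence interval, reported with reasons for stopping or cancellation, elapsed time between samples and sample type. No conclusion about dose-response or a threshold will be drawn.

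Delete the data-driven higher-order terms.

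The cost is one paragraph of text and the loss of a secondary claim that the design cannot support. Assessments, treatment and the primary analysis are unchanged; the additional items to report come from visit dates, sample records and reasons for discontinuation or cancellation that the protocol already has recorded.

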- c. Use each of the alternate readouts as the outcome to obtain estimates of the effect size on each of those assays, and then, fit a reverse regression model to estimate the effect of treatment on *any* of the readouts for which a treatment effect is demonstrated. While many approaches are available for this type of problem, reverse regression has the appealing feature for this small-size trial of not being as overly penalizing as more traditional approaches to the multiplicity problem, such as Bonferroni-like corrections (60). We will also use conventional nonparametric correlation analyses and the intraclass correlation coefficient derived from mixed effects models using each of the readouts to assess how the various readouts relate to one another.
- d. We will then fit models with time-updated total CD4 T cell count as a covariate. These models will allow us to establish how much of the variation in the change of the measured reservoir size is attributable to the expected CD4 T cell increase due to IL-2 administration. We do not believe that, if the magnitude of the effect is similar to the difference observed between the IL-2 alone and the HAART alone groups in the Chun paper, this can be explained simply by a dilutional effect, but this will be tested more formally in this phase of the analysis.

C.2.2. Power and Sample Size Considerations

We base our sample size calculations on the primary analysis using a mixed effect model to estimate the effect of IL-2 administration on the magnitude of the inducible reservoir by QVOA. In the Chun experiment, the difference between the IL-2 and the HAART-only group was 0.64 IUPM, and the variance in the IL-2 group was 0.41. In a 200-simulation run, we estimate that a total sample size of 20 participants will provide an 80% power (95% CI, 0.74-0.84) to detect a difference from baseline to post-IL-2 administration as large as that seen in the Chun paper. Of note, these estimates are likely conservative, since the variation observed in repeated measurements with the optimized version of the QVOA assay that will be used in this study may be lower (variance around 0.11) than that of the assay used in the original Chun report(2).

C.3. INCLUSION CRITERIA

Participants may enroll in the study if they meet the following criteria:

1. Written informed consent signed and dated by study participant.
2. Male or female, at least 18 years of age and not older than 65 years of age.

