The screening visit will occur 8-16 weeks prior to start of rIL-2 treatment, and will include:

- History and complete physical examination that includes evaluation of adequate venous access for leukapheresis
- Height and weight measurements
- Concomitant medication review
- CBC and metabolic panel
- Pregnancy test
- Thyroid function tests and anti-Tpo antibodies
- CD4+ and CD8+ T cell count (both absolute and as percent of lymphocytes).
- Plasma HIV RNA level (using the locally available assay) and verification that plasma HIV RNA levels prior to screening meet the inclusion criteria.
- Hepatitis B and C testing
- Informed consent

D.2.2. Leukapheresis Visit

The pre-treatment leukapheresis visit will occur 4-8 weeks prior to start of rIL-2 treatment, and will include:

- Interval history and targeted physical examination
- Concomitant medication review.
- CBC and metabolic panel
- CD4+ and CD8+ T cell count (both absolute and as percent of lymphocytes) and documentation of all interim CD4+ counts (absolute and percents).
- Thyroid function tests and anti-Tpo antibodies.
- Participant will be instructed as to how IL-2 will be injected subcutaneously. Instructions for preparing rIL-2 for administration are given in the Manual of Operations, which includes the Investigator's Brochure as an appendix. Participants receiving rIL-2 will be taught to give themselves injections. Participants will be given a dosing log for future use and will be encouraged to refer to it during their daily activities. Supporting materials for clinical staff and for participants on administering rIL-2 and managing expected side effects are included in the Manual of Operations. The Manual of Operations also includes contact information for questions concerning clinical management. No rIL-2 will be administered at this visit.
- A 4 liter leukapheresis will be performed at the Seidman Ambulatory Stem Cell Transplant

Unit at University Hospitals using AIDS protocol 328.

- Plasma will be frozen for single copy HIV RNA assay.
- Leukapheresis samples will be processed into PBMC that will be cryopreserved for assays of:
 - HIV reservoir by QVOA
 - HIV reservoir by EDITS
 - Total and intact proviral DNA assay (Accelavir)
 - Immune Cell Phenotype
 - NK cell phenotype

D.2.3. rIL-2 Initial Treatment Visit – Cycle 1, Day 0

The first IL-2 cycle will start 4-8 weeks after the leukapheresis visit and will include:

- Interval history and targeted physical examination, including weight.

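### As worded, secondary analysis (c) applies its multiplicity method only to readouts that have already shown an effect, which undoes most of the protection the method could give

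*Combined protocol and SAP*

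**What the plan says.** Section C.2.1, item (c), works in order. The first step is to "Use each of the alternate readouts as the outcome to obtain estimates of the effect size on each of those assays". The second is a reverse regression for the effect of treatment on any (the plan italicises that word) "of the readouts for which a treatment effect is demonstrated". The next sentence prefers reverse regression in a small trial for "not being as overly penalizing as more traditional approaches to the multiplicity problem, such as Bonferroni-like corrections". Item (c) gives no alpha, no definition of a demonstrated effect and no list of alternates. No other section addresses multiplicity across them.

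The number of alternates has to be pieced together:

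- Section B.3, objective 1, names two: "the intact proviral DNA assay" and EDITS.
- Objective 2 concerns HIV expression "as measured by the EDITS assay and plasma HIV levels", which adds plasma HIV RNA. Section D.2.10 provides for it: "Plasma will be cryopreserved for single copy HIV RNA assay".
- Sections D.2.2 and D.2.10 also list total proviral DNA.

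The count is therefore two to four. All participants receive rIL-2, and section B words its QVOA hypothesis as a reduction "compared to the baseline values in this population". In a reverse regression, treatment can then only mean the time point.

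**The concern.** A joint test limits false positives across several readouts because it considers all of them, including those that show nothing. If only readouts that passed a one-by-one screen on the same data are admitted, the test no longer sees the null results it should weigh against the positive one. A chance change on a single assay would usually survive the second step. It could then be reported as having passed the one procedure the plan justifies by reference to multiplicity. The alternates serve secondary objectives 1 and 2, so such a result could be read as support for an effect on the reservoir.

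**Working it through.** **Inputs.** From the documents: a before/after comparison in one arm; 20 participants (section C.2.2; the synopsis gives 16); K = 2 to 4 alternates. Assumed, because the documents are silent: two-sided 0.05 at both steps; a common correlation r between change scores, from 0 to 0.8; normal change scores; and a paired Hotelling test in place of the reverse regression. The plan states no error rate for (c), so there is no figure to reproduce.

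**Benchmark.** With independent readouts and no correction, the chance of at least one false positive is 1 − 0.95^K:

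- K = 2: 1 − 0.9025 = 9.75%
- K = 3: 1 − 0.8574 = 14.3%
- K = 4: 1 − 0.8145 = 18.5%

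**Mechanism.** If one readout passes the screen, Hotelling's T² on that readout equals t², so the second step repeats the first test and must reject. Under the null this is the usual case. Exactly one readout is selected in 90-97% of chance selections with K = 2 and in 80-92% with K = 4 (r = 0.5 and r = 0). At r = 0.8 the shares are 74% and 58%.

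**Simulation.** Global null, n = 20, 100,000 trials per setting. A is the percentage of trials with any readout selected. C is the percentage in which the joint test on the selected readouts also rejects.

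| K | Rate (%) | r=0 | 0.3 | 0.5 | 0.6 | 0.8 |
|---|---|---|---|---|---|---|
| 2 | A | 9.6 | 9.5 | 9.1 | 8.7 | 7.9 |
| 2 | C | 9.6 | 9.5 | 9.0 | 8.5 | 7.1 |
| 3 | A | 14.2 | 13.9 | 12.6 | 11.9 | 10.0 |
| 3 | C | 14.2 | 13.7 | 12.2 | 11.2 | 8.2 |
| 4 | A | 18.4 | 17.2 | 15.8 | 14.6 | 11.7 |
| 4 | C | 18.4 | 17.0 | 15.0 | 13.3 | 8.7 |

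A joint test of all K readouts with no screen gives 4.9-5.1% throughout. With n = 12 or 16 (K = 2 and 4, r = 0 and 0.8), C is 7.1-18.6%, so a smaller sample does not change the picture.

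**Share of protection lost**, (C − 5)/(A − 5):

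- r = 0.5: K = 2, 4.0/4.1 = 98%; K = 3, 7.2/7.6 = 95%; K = 4, 10.0/10.8 = 93%.
- r = 0.8: K = 2, 2.1/2.9 = 72%; K = 3, 3.2/5.0 = 64%; K = 4, 3.7/6.7 = 55%.

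**A form closer to reverse regression.** Matched-pair conditional logistic regression with a likelihood-ratio test (20,000 trials, n = 20):

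| K | All readouts, no screen (%) | After screen, r=0 | r=0.5 | r=0.8 |
|---|---|---|---|---|
| 2 | 6.5-6.8 | 9.6 | 9.1 | 7.6 |
| 3 | 7.6-7.7 | 14.4 | 12.3 | 9.0 |
| 4 | 9.2-9.3 | 18.7 | 16.0 | 9.3 |

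This test is oversized at n = 20 even without a screen. At r = 0 the screen accounts for most of the excess over 5%. At r = 0.8 much of the excess is already present without it, and with K = 4 practically all of it is.

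**The case against.** Four points can be made for the plan.

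- **No family-wise error rate is claimed.** Item (c) says only that reverse regression penalises less than Bonferroni-type corrections. This stands: a reader might infer that the plan promises error control and breaks the promise, but the promise is implied at most. The sentence does still justify the method as an approach to multiplicity.
- **The italicised any may signal a global test of all readouts.** That is possible. On that reading the restricting clause contradicts the intent, and deleting it is still the right correction.
- **The size depends on unstated quantities.** It does. The 18% figure needs four independent readouts, and intact and total proviral DNA are listed as one assay on the same specimen, so zero correlation is an outer bound. A strict screen would control the error: at 0.0125 the two-step rate is 2.2-4.8%. With four readouts, however, that is Bonferroni applied at the screen, and the plan states no such threshold.
- **In the conditional-logistic form at high correlation, the clause is not the main cause.** This also stands. Attributing the whole excess to selection would be wrong there.

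A reader might also infer that effect sizes will be overstated. The documents do not support that, because (c) already calls for an estimate on every alternate. Overstatement would arise only if selected results were reported in place of those estimates.

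**Conclusion.** The concern holds in limited form. As worded, (c) screens and tests on the same data. Under an assumed two-sided 0.05 screen at n = 20, the false-positive rate is about 7-10% for the two alternates named in objective 1 and about 9-18% for four, against about 5% for an unscreened joint test. Nearly all the protection is lost at correlations up to 0.5, and about half to three quarters at 0.8. These figures rest on the assumed threshold, correlation, number of readouts and Hotelling stand-in. Severity is minor: this is a secondary analysis in a pilot, and neither the primary QVOA test nor the planned unselected estimates are affected.

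**What to change.** In the phrase "of the readouts for which a treatment effect is demonstrated", delete everything after the word readouts. List the alternates and the alpha in advance, and apply the joint before/after analysis to all of them whatever their individual results.

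Use a small-sample reference such as sign-flip permutation, flipping each participant's whole vector of changes together. Its simulated size at n = 20 is 4.6-5.6%. It is valid if changes are symmetric about zero under the null, which may be doubtful where a 120 cc draw replaces the final leukapheresis (section D.2.10). If reverse regression is kept as the statistic, take its p-value from the sign flips.

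If one statistic is to be fixed, the largest |t| is the safer default. With an assumed change of 0.7 SD in every readout, four readouts and r = 0.6, the quadratic (Hotelling-type) form has power 0.74 against 0.89 for plain Bonferroni; across the settings run with all readouts responding, the largest |t| has 0.87-0.98. The largest |t| can also use every available pair. If 4 of 20 participants each miss one assay (assumed; four readouts, one responder, r = 0), its power is 0.63 against 0.43 for the quadratic form on complete vectors.

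Alternatively, keep the selection, label (c) exploratory and drop the multiplicity rationale.

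The cost is SAP wording, a few lines of code and some power. With one responder the largest |t| has power 0.66-0.77, while the two-step rule has about 0.85 at r = 0; part of that gap reflects the two-step rule's inflated error rate. No version removes time drift from a single-arm before/after comparison.
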